This section outlines the statistical analysis strategy and procedures for the study. If, after the study has begun, changes are made to primary and/or key secondary hypotheses, or the statistical methods related to those hypotheses, then the protocol will be amended (consistent with ICH Guideline E-9). Changes to exploratory or other non-confirmatory analyses made after the protocol has been finalized, along with an explanation as to when and why they occurred, will be listed in the Clinical Study Report (CSR) for the study. Post hoc exploratory analyses will be clearly identified in the CSR. A separate Statistical Analysis Plan (SAP) with further details than presented here will be finalized prior to first patient enrolled to minimize any bias, as the study is non-blinded.

Power and Sample Size

The determination of sample size for this study is based on the primary objective to demonstrate the superiority of the IrriSept irrigation unit versus conventional standard of care in patients who undergo open abdominal laparotomy for abdominal trauma or acute surgical abdomen within 36 hours of initial presentation to their healthcare organization. The primary endpoint is the rate of SSI observed within 30 days (+/- 3 days) from the date of the index operation.

Based on historical data, it is assumed that the rate of SSI within the standard of care group will be \geq 20%. A total of 600 patients (300 per group) will provide \geq 90% power to demonstrate a reduction in the rate of SSI, up to 50%, assuming a control group rate for SSI of \geq 20%, based on a two-sided Chi-square test with a 5% significance level. The following table shows the power achieved under various combinations of control group SSI rates and relative treatment differences.

Table 2.1: Power associated with a total sample size of 600 (n=300/group), based on a two-sided Chi-square test with a 5% significance level.

Control Group SSI	Relative Treatment Difference (IrriSept/Control)		
Rate	50% Reduction	40% Reduction	30% Reduction
15%	83%	62%	38%
20%	93%	76%	50%
25%	98%	87%	61%

It is anticipated that approximately 1100 patients will be screened, 650 patients will be enrolled, to obtain 600 evaluable patients, based on a non-evaluable rate of approximately 5%. All calculations were carried out in SAS version 9.2 using the comparison for two independent proportions procedure in PROC POWER.

Study Number IRR-CT-901-2013-01	Version: 1.0	01AUG2014

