© Confidential IrriMax Corporation		Page 28 of 35

Analysis Populations

Intention-to Treat (ITT)

The intention-to-treat population will be defined as all randomized subjects. Subjects will be assigned to a group based on the group they were randomized to.

Per-Protocol Population (PP)

Within the ITT population, subjects will be considered evaluable if they completed the 30 day follow up visit. Subjects who are withdrawn from the study prior to the 30 day follow up will be designated "non-evaluable" and excluded from the PP population.

Safety Analysis Set (SAS)

The safety analysis set will consist of all randomized subjects who underwent an emergency operation. The safety analysis set will be used for all safety analyses. Subjects will be assigned to a group based on the actual procedure received.

Efficacy Analyses

Primary Endpoint

For the primary endpoint, the number and proportion of patients with a SSI observed within 30 days from the date of emergency operation will be summarized by treatment group, along with the difference and 95% confidence interval for the difference (based on the Wald method). If a patient is missing their end of study assessment, or if they died prior to the end of study assessment, they will be classified as having met the primary endpoint of a SSI. A comparison between treatment groups will be made using the Cochran-Mantel-Haenszal test, stratified by site. The two-sided p-value, the adjusted relative risk (IrriSept/Control) and 95% confidence interval of the relative risk (based on the Wald method) will be reported. The study will be deemed successful if the two-sided p-value for the end of study treatment difference is < 5%.

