Concomitant medications are medications that are taken at any time after enrollment. Concomitant medications will be coded using the WHO Drug Dictionary and summarized by drug class and preferred term for each treatment group. The summaries will present the number and percentage of patients using each medication in each treatment group. Patients may have more than one medication per preferred term. At each level of summarization, a patient is counted once if he/she reported one or more medications at that level.

Disposition

A clear accounting of disposition including, the number and percentage of patients screened, randomized, and completed, as well as the primary reasons for screen failure and reasons for early discontinuation of therapy will be reported overall and by treatment group.

Subjects who withdraw from the study (either voluntarily or involuntarily) or do not complete the required End of Study visit will be designated as "non-evaluable." Any data collected on these subjects will not be used in the final efficacy analysis. For those who withdraw consent, screen fail information will be collected. For those subjects lost to follow-up will be noted in the database as early termination. Subjects who are classified as "non-evaluable" will be replaced to the extent required to enroll 600 evaluable subjects.

Study Number IRR-CT-901-2013-01	Version: 1.0	01AUG2014
© Confidential IrriMax Corporation		Page 31 of 35

Interim Analyses

An interim analysis is planned when approximately 33% and 66% of the total number of patients has been enrolled. The purpose of these interim analyses is to monitor safety and study conduct. At the second interim analysis, the sample size will be re-estimated using the conditional power approach.

All persons involved in the conduct and analysis of the study will remain blinded to the results of the interim analysis.

Test Material Compliance and Accountability:

An initial supply of Study Product will be supplied to the study site, by IrriMax Corporation, at least one (1) week prior to study commencement.

Procedures and instructions for Study Product dispensing and accountability will be provided in the Investigator Site Binder.

Investigator Site Responsibilities:

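### Primary SSI test has two conflicting rules for patients without a 30-day assessment and no named analysis population; the stated power of at least 90% fits only one rule

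*Combined protocol and SAP*

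**What the plan says.** All references are to the combined protocol and SAP.

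- **Efficacy Analyses, Primary Endpoint.** "If a patient is missing their end of study assessment, or if they died prior to the end of study assessment", the patient is an event: "they will be classified as having met the primary endpoint of a SSI". The test is a site-stratified Cochran-Mantel-Haenszel (CMH) test, and success is a two-sided p-value below 5%.
- **Analysis Populations.** ITT is every randomised subject. For PP, "subjects will be considered evaluable if they completed the 30 day follow up visit". Only the safety set is tied to any analysis.
- **Disposition.** Subjects who withdraw "or do not complete the required End of Study visit will be designated as" non-evaluable. Then: "Any data collected on these subjects will not be used in the final efficacy analysis". They "will be replaced to the extent required to enroll 600 evaluable subjects".
- **Power and Sample Size.** 300 per group, control SSI rate of at least 20%, a 50% relative reduction and a two-sided 5% chi-square test. Stated power is at least 90% (93% in Table 2.1). Enrolment is 650 for 600 evaluable, with a non-evaluable rate of about 5%.
- **Visit 2: End of Study.** Assessments may be done by telephone, drawing on an earlier standard-of-care visit. For a subject who has died, the site completes what it can of the CRF.
- **Interim Analyses.** "At the second interim analysis, the sample size will be re-estimated using the conditional power approach".
- **Statistical Methods.** A separate, more detailed SAP "will be finalized prior to first patient enrolled to minimize any bias".

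**The concern.** A randomised patient who withdraws or is lost is an SSI under one section and absent from the analysis under another. No sentence says which section governs the p-value that decides success. The trial is open-label, and the protocol itself gives that as the reason to fix the analysis before enrolment. Leaving the event rule open works against that aim.

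Three things follow.

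- Two analysts could follow the document faithfully and report different primary results.
- The power statement uses 300 evaluable patients per arm and no imputed events. It matches the exclusion rule and overstates power under the missing-as-SSI rule, because imputed events added to both arms dilute the relative effect.
- The conditional-power re-estimation needs an event rule and is not given one.

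The status of a telephone Visit 2 is also open. The text does not say whether it counts as the assessment in the Primary Endpoint rule or as the completed visit in the PP definition.

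**Working it through.** **Where the two rules meet**

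| Patient | Primary Endpoint section | Disposition section |
|---|---|---|
| Withdrew or lost, no assessment | SSI | Excluded and replaced |
| Died before Visit 2 | SSI | Not mentioned; excluded only by inference |
| Telephone Visit 2 only | Not stated | Not stated |

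The conflict is express in the first row and inferred in the second.

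**Reproducing the plan's power.** For n per arm and rates p1, p2 with mean p̄:

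power = Φ{[(p1 − p2) − 1.96·√(2p̄(1−p̄)/n)] / √(p1(1−p1)/n + p2(1−p2)/n)}

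At 0.20 v 0.10 and n = 300: (0.10 − 1.96 × 0.02915)/0.02887 = 1.485, so power is 93.1%. All nine cells of Table 2.1 reproduce.

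**Power if missing counts as SSI.** Let m be the share imputed, equal in both arms and unrelated to SSI. Each rate becomes p′ = p(1 − m) + m. At m = 0.05:

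- control: 0.20 × 0.95 + 0.05 = 0.240
- IrriSept: 0.10 × 0.95 + 0.05 = 0.145
- relative risk: 0.145/0.240 = 0.60 instead of 0.50

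Number randomised: 600/0.95 = 632 (316 per arm), or the stated 650 (325 per arm).

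- n = 316: (0.095 − 1.96 × 0.03137)/0.03114 = 1.077, power 85.9%
- n = 325: (0.095 − 1.96 × 0.03093)/0.03070 = 1.120, power 86.9%

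An exact-binomial calculation gives 86.1% and 87.2%. A simulated CMH test with 650 patients in 13 equal sites gives 87.2%.

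**Sensitivity (20% v 10% unless stated)**

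| Scenario | n per arm | Power |
|---|---|---|
| None imputed, as designed | 300 | 93.1% |
| 3% imputed | 325 | 90.3% |
| 5% imputed | 316 / 325 | 85.9% / 86.9% |
| 5% imputed, all otherwise SSI-free (p′ = p + 0.05) | 316 / 325 | 88.3% / 89.2% |
| 7.7% imputed (50/650): 26.2% v 16.9%, RR 0.65 | 325 | 81.8% |
| 25% v 12.5%, 5% imputed | 325 | 95.2% |

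Power stays at 90% or more if imputed loss is at most 2.7% (316 per arm) or 3.2% (325 per arm). At 5% loss it also stays there if the control rate is at least 21.9% (316) or 21.5% (325), with a 50% reduction.

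**Effect on the verdict (unstratified Pearson chi-square).** At the design counts, 60/300 v 30/300, p = 0.0006. After adding imputed events:

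- 16 per arm (76/316 v 46/316): p = 0.0025
- 25 per arm (85/325 v 55/325): p = 0.0042
- 20 control, 30 IrriSept (80/320 v 60/330): p = 0.035
- 30 control, 20 IrriSept (90/330 v 50/320): p = 0.0003

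None crosses 0.05. With 60/300 control events and 16 imputed per arm, the verdict changes at only two IrriSept counts: 40 events (p from 0.028 to 0.0503) and 41 events (0.038 to 0.064).

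**How often the rules disagree.** Each of 100,000 simulated trials was analysed under both rules, with 5% loss and site-stratified CMH. Thirteen equal sites were assumed; the protocol plans 12 to 14.

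| True rates | n per arm | Power, excluded | Power, missing = SSI | Disagree on p < 0.05 |
|---|---|---|---|---|
| 20% v 10% | 316 | 93.5% | 86.3% | 9.1% |
| 20% v 12% | 316 | 76.8% | 66.5% | 15.5% |
| 25% v 12.5% | 325 | 98.1% | 95.4% | 3.4% |
| 20% v 20% | 325 | 5.2% | 5.1% | 3.9% |

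Of the 9.1%, 8.2 points are significant only under exclusion and 0.9 only under missing-as-SSI. Type I error is about 5% under either rule.

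**The case against.** The natural reading is that missing-as-SSI is primary. It sits beside the success criterion, whereas non-evaluable is a term from the PP definition that Disposition merely reuses. The separate SAP, not in the supplied text, may settle it. That is probably the intent, but the Disposition sentence speaks of the final efficacy analysis without limiting itself to PP, and the sample size follows it. A SAP that adds detail does not remove a contradiction between protocol sentences.

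On power, the 93% is right on its own inputs. The shortfall needs the missing-as-SSI rule, a control rate at the 20% floor, and the full 5% imputed. Telephone visits could reduce true missingness; at 2% imputed, power is 91% to 92%. This stands as a condition on the figure. But the protocol defines non-evaluable by not completing the visit, so its 5% is a fair measure of who would be imputed.

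The 7.7% case is weaker. The Study Summary describes about 650 completed and 600 evaluated, whereas Power and Sample Size says 650 enrolled. The 82% figure depends on the second reading.

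Loss unrelated to SSI is also open to doubt. Subjects who later meet an exclusion criterion are removed, and one criterion is reoperation through the same incision within 30 days. Such removals may be linked to infection. The documents do not allow the direction or size of that effect to be fixed, so 86% to 87% is illustrative.

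**Conclusion.** The concern holds. The conflict for withdrawals and non-completers, together with the unnamed primary population, must be fixed before the primary test can be called prespecified. For deaths, the conflict is an inference.

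The power restatement is secondary and conditional: about 86% to 87% instead of at least 90%, if missing counts as SSI, the control rate is 20%, the reduction is 50%, and 5% are lost equally and independently of SSI. It disappears at about 3% imputed with 325 per arm, or at a control rate of about 22%. A clear result such as 60 v 30 events survives either rule in every scenario tried; a closer one may not.

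**What to change.** 1. Name ITT (all randomised) as the primary population, with missing assessment or prior death counted as SSI. Limit the Disposition exclusion sentence to PP. Say whether a death before Visit 2 is non-evaluable for PP, and how subjects removed after randomisation are classified. Carry the same wording into the separate SAP.
2. State that a telephone Visit 2, with any earlier standard-of-care data it draws on, counts as the end-of-study assessment and as a completed visit.
3. Make PP the sensitivity analysis, defined by visit completion and not by known SSI status, so that events are not selectively kept. Report documented SSI, deaths and missing separately by arm.
4. Restate power at 20% v 10% as about 86% to 87% with 5% imputed (82% at 7.7%, if the 650 are enrolled and not completed), with the assumptions. Require the sample-size re-estimation to use the same event rule.
5. Wording: say whether the missing/death rule applies to readmission, which borrows the primary methods. Describe the 50% reduction in the power sentence as a minimum, since Table 2.1 gives 76% for a 40% reduction at a 20% control rate. Align 650 with the 5% rate (632) or state 7.7%.

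The cost is text and one table on a population already defined. More patients are needed only if the sponsor wants 90% power at 20% v 10% under missing-as-SSI: about 360 per arm at 5% imputed, or 415 at 7.7%. The planned re-estimation could address that. The drawbacks are a less favourable power statement and primary rates above documented SSI in both arms, hence the separate rows.

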During the SIV, site personnel will receive the following training and documents:

- Protocol and Tool Kit Training
- 2. Review of Informed Consent Form process
- 3. Adverse Events/Serious Adverse Event Reporting Forms and Process
- 4. Responsibilities of the Principal Investigator and study staff
- 5. Source Document/CRF Completion Guidelines
- 6. Proper Use and Storage of the Study Product
- 7. Regulatory Binder Review
- 8. Miscellaneous

STUDY PROCEDURES:

Visit 1: Screening Phase

The following data will be collected once consent has been obtained and the subject is deemed eligible for enrollment by the Principal Investigator or designee.

- Date and time subject presents to the Facility
- Subject demographics (Date of Birth, Gender, Height, Weight)
- Abbreviated Injury Scale (AIS) and/or Glasgow Coma Scale (GCS)
- Surgical Risk Factors
- Present On Admission (POA) risk factors
- Record relevant collected laboratory values as per CRF
- Denote any Screening Phase Protocol Deviations

Study Number IRR-CT-901-2013-01	Version: 1.0	01AUG2014
© Confidential IrriMax Corporation		Page 19 of 35

Visit 1: Perioperative Phase

The Perioperative Phase will begin when preoperative activity is initiated and will conclude when the subject leaves the post-anesthesia care unit. Acutely ill subjects may bypass recovery and receive post-anesthesia care in the Intensive Care Unit (ICU). The end of the perioperative phase will be defined as when the patient is "handed off" and report is given to the ICU or surgical floor staff.

Pre-Operative Assessments

Pre-Op Assessment information will be collected and documented in the subject's hospital chart and transcribed to the corresponding case report form (CRF). Pre-Op Assessments include:

- Type of prophylactic antibiotic administered
- Time of prophylactic antibiotic administration
- ASA Physical Status Classification System score
- Whether or not a warming strategy (device or other means) was initiated prior to surgery
- Randomization of subject to Standard of Care irrigation or IrriSept system

Intra Operative Assessments/Procedures

The first assessment is completed immediately after subject is admitted to the Operating Room (OR). OR Assessments include:

- Date and Time surgical procedure started
- Subjects randomized to the IrriSept system will receive irrigation specific to the IrriSept study kit IFU.

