It is anticipated that treatment groups will be well balanced with respect to baseline and demographic characteristics as well as risk factors for SSI, however if there are imbalances these will be accounted for in a supportive analysis using logistic regression. In these analyses, a logistic regression model with treatment as a fixed categorical variable and key baseline/demographic variables that are imbalanced will be included in the model to obtain adjusted estimates of the treatment effect in the form of odds ratios with two-sided 95% confidence intervals. Identification of variables to include will be based on comparisons between the two groups using appropriate two-sided tests based on the underlying distribution of the data. Those variables that are found to be significant (p < 0.05) will be included in the model.

Secondary Endpoints

The rate of readmission within 30 days from the date of the abdominal surgical procedure will be analyzed using the same methods as described for the primary endpoint.

The length of stay in the hospital will be calculated as the difference between the date of discharge and the date of admission, plus 1 day. Length of stay will be summarized by treatment group using descriptive statistics. As length of stay data tends to be highly skewed, a comparison of the LOS between the two treatment groups will be made by modeling the log LOS using a mixed effect model with a fixed effect term for treatment and a random component for center. This means and 95% confidence intervals for the difference between treatment groups will be back transformed and presented along with the two-sided p-value from a two-sample t-test.

An additional analysis will seek to define risk-adjusted length of stay outliers and whether there are observed differences between the two study populations. Using the post-operative length of stay as the dependent variable, a linear model will be used by employing those patients in the study who had no complications identified through the entire 30 day postoperative period. Again, hospital variables will be used. The observed length of stay for all patients will then be compared to the expected length of stay from the model to determine

Study Number IRR-CT-901-2013-01	Version: 1.0	01AUG2014
© Confidential IrriMax Corporation		Page 29 of 35

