Univariate assessment of categorical risk factors and of continuous risk factors will be assessed to identify whether differences exist between the two populations of patients in the frequency of independent variables following patient randomization. Risk factors with P<0.05 on univariate analysis will then be used to create a forward stepwise logistic regression model to predict SSI. Hospital dummy variables will be employed to remove hospital effects. Logistic coefficients will be defined for the clinical variables including the use of the IrriSept irrigation system. Odds ratios and confidence intervals will be established to evaluate statistical significance, or lack thereof, of the IrriSept system. An additional benefit of this modeling will be the development of risk equations that combine administrative, clinical, and laboratory data into the prediction of SSI in this population of patients.

Multiplicity

As there is a single primary endpoint, and no formal unblinded interim analyses that will utilize the primary endpoint to modify the trial, no adjustment for multiplicity is planned. No adjustment for multiplicity is planned for the analysis of secondary endpoints

Sub-groups

To determine whether the treatment effect is consistent across various subgroups, the estimate of the odds ratio (and 95% CI) for the primary endpoint will be estimated and displayed using forest plots for the following sub-groups:

- Age category (≤65 vs. >65 years)
- Gender (female, male)
- Emergency laparotomy for trauma exclusively vs. laparotomy for emergency general surgery

For the analysis of each sub-group, a logistic regression model for the primary endpoint will be used, with terms for treatment group, the sub-group and the sub-group by treatment interaction. The odds ratios and 95% CI's within each sub-group category will be reported, along with the p-value for the interaction term.

Safety Analyses

All safety analyses will be presented using the safety analysis set. No formal hypothesis testing will be conducted.

Adverse Events

Adverse events will be coded using MedDRA (Version 17.x). All AEs that occur after the start of surgery (cut time) will be summarized using frequency counts and percentages. Summaries will be presented by treatment

Study Number IRR-CT-901-2013-01	Version: 1.0	01AUG2014
© Confidential IrriMax Corporation		Page 30 of 35

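### The primary SSI test is valid, but the plan has no prespecified covariate-adjusted estimate on the primary's risk scale, so the supportive odds ratio cannot show whether imbalance explains the primary result

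*Combined protocol and SAP*

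**What the plan says.** Under Efficacy Analyses, Primary Endpoint: "A comparison between treatment groups will be made using the Cochran-Mantel-Haenszal test, stratified by site". The effect is reported as a risk difference and as a site-adjusted relative risk, both with Wald intervals, and success is a two-sided p-value below 5%. The Randomization section allocates 1:1 in the operating room, stratified by centre only.

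Patient-level covariates appear in three other places:

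- **Supportive analysis (same section).** If the arms are imbalanced, a logistic regression gives "adjusted estimates of the treatment effect in the form of odds ratios with two-sided 95% confidence intervals". Candidate variables are tested between arms, and those with p < 0.05 enter. Treatment and the imbalanced variables are the only terms named; site is not among them.
- **Exploratory Analyses.** A forward stepwise logistic model with hospital dummy variables, reported as odds ratios.
- **Sub-groups.** One of three factors is "Emergency laparotomy for trauma exclusively vs. laparotomy for emergency general surgery", again analysed with odds ratios.

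Demographics and Baseline Summaries says that baseline comparability will be described without hypothesis tests.

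Indication is inclusion criterion 3. An ASA score of five or more is exclusion criterion 3, and "ASA Physical Status Classification System score" stands in the Pre-Operative Assessments list ahead of the randomisation item. Both are therefore available before allocation.

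Statistical Methods refers to a separate, more detailed SAP. The document supplied contains only the protocol's statistical section, so this point is limited to that text.

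**The concern.** The supportive analysis exists to show whether a chance imbalance accounts for the primary result. To do that, it must estimate the same quantity as the primary analysis and differ only in the adjustment. As planned it differs in three other ways: it uses odds rather than risks, it lists no site term, and its covariates are chosen by a significance test rather than by prognostic importance. If the two results disagree, a reader cannot tell imbalance from arithmetic. In most trials the two obvious candidates, indication and ASA class, would not be adjusted for at all. The plan also contradicts itself on whether baseline tests will be done.

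**Working it through.** **1. The plan's own power figure.** Inputs from Power and Sample Size: 300 per group, 20% v 10%, "based on a two-sided Chi-square test with a 5% significance level". With pooled variance and mean risk 0.15:

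- SE under the null = √(2 × 0.15 × 0.85/300) = 0.02915
- SE under the alternative = √((0.20 × 0.80 + 0.10 × 0.90)/300) = 0.02887
- z = (0.10 − 1.96 × 0.02915)/0.02887 = 1.485, so power = 93.1%

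Table 2.1 states 93%. All nine cells reproduce within 0.5 point (20% v 12%: 76.3% against 76%). The sample size calculation is not in question.

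**2. Scale gap at the design rates.** OR = [p₂/(1−p₂)]/[p₁/(1−p₁)].

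| Control v IrriSept | RR | OR |
|---|---|---|
| 20% v 10% | 0.50 | 0.1111/0.2500 = 0.44 |
| 20% v 12% | 0.60 | 0.1364/0.2500 = 0.55 |
| 25% v 12.5% | 0.50 | 0.1429/0.3333 = 0.43 |

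The primary rule counts missing assessments as SSI. With 5% missing in each arm, 20% v 10% becomes 0.95 × 20 + 5 = 24% v 0.95 × 10 + 5 = 14.5%, which is RR 0.60 but OR 0.54.

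**3. Shift under perfect balance.** Assume control risks of 10% in trauma and 30% in acute abdomen, with half of each arm in each group. A common OR of 0.427 within groups gives odds of 0.1111 × 0.427 = 0.0474 and 0.4286 × 0.427 = 0.1830, that is, risks of 4.5% and 15.5%, averaging 10.0%. The overall comparison is still 20% v 10%: RR 0.50, unadjusted OR 0.44. The adjusted OR is 0.43 with no imbalance to correct. The standardised RR stays at 0.50.

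A simulation covered indication and ASA together: 600 patients, 13 equal sites, 2,000 trials per setting, 50/50 indication, 40% ASA 3-4, site SD 0.3 on the logit scale, and an SSI odds ratio of 1, 1.5, 2 or 3 for each factor. All these strengths are assumed. Where RR is 0.50, the average fitted adjusted OR ran from 0.43 to 0.40 (underlying values 0.44 to 0.41; the rest is small-sample bias). Where RR is 0.60 it ran from 0.53 to 0.50. The standardised RR averaged 0.49-0.50 and 0.60.

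**4. The entry rule.** Under sound randomisation a covariate passes p < 0.05 with probability 0.05. Treating the two as independent, the chance that indication or ASA enters is 1 − 0.95² = 9.75%, so in about 90% of trials neither does. If 12 independent covariates are screened (the synopsis lists 12 patient risk factors), the chance that at least one enters is 1 − 0.95¹² = 46%. The model would then often be run on variables picked by chance.

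**5. What adjusting the primary test would gain.** Same simulation, power in %, for factor odds ratios 1 / 1.5 / 2 / 3:

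| | 20% v 10% | 20% v 12% |
|---|---|---|
| CMH by site | 94.0 / 93.3 / 93.8 / 93.6 | 75.4 / 75.8 / 76.2 / 76.6 |
| Logistic: site, indication, ASA | 94.2 / 93.4 / 94.6 / 95.5 | 75.8 / 77.0 / 77.8 / 78.6 |
| CMH, site × indication × ASA | 92.2 / 91.9 / 92.6 / 93.7 | 72.4 / 73.8 / 74.2 / 77.0 |

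The model gains about 0 to 2 points. With uneven sites it gained about 0 to 4.5 points, with type I error of 5.4-5.7% against about 5% for CMH. Crossing the factors into 13 × 2 × 2 = 52 strata usually loses power.

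**The case against.** The strongest reply is that the primary analysis is sound. CMH by site matches the only randomisation stratum and fits the chi-square powering. A reader might infer that leaving out indication and ASA makes the primary test wrong or badly inefficient. The documents do not support that: they give no SSI rates by indication or ASA class, and under assumed strengths the gain is modest. A replacement model would fit about 16 parameters (13 for sites, then treatment, indication and ASA) to 60 + 30 = 90 events, or 5.6 events each. Centres are capped at 120 subjects but have no minimum, so zero-event sites are possible; CMH simply gives these no weight. This objection stands, and it is why the primary test should not be faulted.

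A reader might also infer that the supportive result is bound to look stronger than the primary. That does not follow either. Adjusting for an imbalance that favoured IrriSept moves the OR towards 1, and in most trials neither indication nor ASA enters. The shift from 0.44 to 0.40-0.43 is small beside the sampling error: for 60 v 30 events, SE(log OR) = √(1/60 + 1/240 + 1/30 + 1/270) = 0.241, a 95% interval of about 0.28 to 0.71.

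It can be said too that a notable imbalance in indication would trigger the rule. The SD of the arm difference is √(4 × 0.25/600) = 4.1 points, so a 2-SD imbalance of 8 points gives p of about 0.046 and indication would enter. With assumed risk gaps of 10 to 20 points it shifts the risk difference by 0.8 to 1.6 points, against a standard error of 2.9. This is fair, but the adjusted answer would still come as an odds ratio, which leaves the comparison problem untouched.

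**Conclusion.** The point holds as a weakness of interpretation in the supportive analysis, not as an error in the primary test. The plan holds two patient-level adjusted models, one supportive and one exploratory. Both report odds ratios, and neither has a fixed covariate set. No covariate-adjusted risk difference or relative risk is prespecified. The scale gap (0.44 against 0.50, 0.55 against 0.60) is arithmetic at the plan's own rates. The further move to about 0.40-0.43 and the power gain of about 0 to 4.5 points rest on assumed prognostic strengths. The figure of about 10% assumes sound randomisation and independent tests. The conflict between the p < 0.05 selection rule and the statement that no baseline tests will be performed is in the text and needs reconciling in any case.

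**What to change.** In the supportive paragraph of Primary Endpoint, replace selection by p < 0.05 with a prespecified logistic model containing treatment, site, indication (trauma v acute abdomen) and ASA class, run whatever the observed balance. Report from it the standardised (marginal) risk difference and relative risk with 95% confidence intervals, naming the method (delta or bootstrap). State a rule for pooling small or zero-event sites. This also removes the conflict with Demographics and Baseline Summaries as far as the supportive analysis is concerned.

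Keep the site-stratified CMH p-value as the success criterion. Making the adjusted model primary is optional; if it is considered, check type I error with many small sites first. Do not add indication and ASA as crossed CMH strata.

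The cost is new wording and slightly more analysis work, with no new data, since both covariates are already collected. It is best settled before first enrolment, when the plan says the SAP will be final because the study is not blinded.
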